5.3. Repeated Measurements in Spirometry Data

If there are multiple valid assessments in spirometry data at a particular visit, the highest value will be chosen for analysis.

5.4. Absolute and Relative Change from Baseline

The absolute change from baseline at each post-baseline visit is calculated as (post-baseline value – Baseline), while the relative change (%) from baseline at each post-baseline visit is calculated as (post-baseline value – Baseline)/Baseline×100.

5.5. Missing Dates of AE and Prior and Concomitant Medications

5.5.1. Missing Date Information for Adverse Events

The following imputation rules only apply to cases in which the start date is incomplete (ie, partially missing) for adverse events.

Missing day and month

- If the year is same as the year of the date of the first dose of double-blind study drug, then the day and month of the date of the first dose of double-blind study drug will be assigned to the missing fields.
- If the year is prior to the year of the date of the first dose double-blind study drug, then December 31 will be assigned to the missing fields.
- If the year is after the year of the date of the first dose double-blind study drug, then January 1 will be assigned to the missing fields.

Missing month only

- The day will be treated as missing and both month and day will be replaced according to the above procedure.

Missing day only

- If the month and year are same as the year and month of the date of the first dose double-blind study drug, then the date of the first dose double-blind study drug will be assigned to the missing day.
- If either the year is before the year of the date of the first dose of double-blind study drug or if both years are the same but the month is before the month of the date of the first dose of double-blind study drug, then the last day of the month will be assigned to the missing day.
- If either the year is after the year of the date of the first dose of double-blind study drug or if both years are the same but the month is after the month of the date of the first dose of double-blind study drug, then the first day of the month will be assigned to the missing day.

If the stop date is complete and the imputed start date as above is after the stop date, the start date will be imputed by the stop date.

5.5.2. Missing Date Information for Prior or Concomitant Medications

For prior or concomitant medications, including rescue medications, incomplete (ie, partial missing) start date and/or stop date will be imputed. When the start date and the stop date are both incomplete for a subject, impute the start date first.

5.5.2.1. Incomplete Start Date

The following rules will be applied to impute the missing numerical fields. If the stop date is complete and the imputed start date is after the stop date, then the start date will be imputed using the stop date.

Missing day and month

- If the year of the incomplete start date is the same as the year of the date of the first dose of double-blind study drug, then the day and month of the date of the first dose of double-blind study drug will be assigned to the missing fields.
- If the year of the incomplete start date is prior to the year of the date of the first dose of double-blind study drug, then December 31 will be assigned to the missing fields.
- If the year of the incomplete start date is after the year of the date of the first dose of double-blind study drug, then January 1 will be assigned to the missing fields.

Missing month only

- The day will be treated as missing and both month and day will be replaced according to the above procedure.

Missing day only

- If the month and year of the incomplete start date are the same as the month and year of the date of the first dose of double-blind study drug, then the day of the date of the first dose of double-blind study drug will be assigned to the missing day.
- If either the year is before the year of the date of the first dose of double-blind study drug or if both years are the same but the month is before the month of the date of the first dose of double-blind study drug, then the last day of the month will be assigned to the missing day.
- If either the year is after the year of the date of the first dose of double-blind study drug or if both years are the same but the month is after the month of the date of the first dose of double-blind study drug, then the first day of the month will be assigned to the missing day.

5.5.2.2. Incomplete Stop Date

The following rules will be applied to impute the missing numerical fields. If the date of the last dose of double-blind study drug is missing, replace it with the last visit date or data cut-off date if the subject is on-going. If the imputed stop date is before the start date (imputed or non-imputed start date), then the imputed stop date will be equal to the start date.

Missing day and month

- If the year of the incomplete stop date is the same as the year of the date of the last dose of double-blind study drug, then the day and month of the date of the last dose of double-blind study drug will be assigned to the missing fields.
- If the year of the incomplete stop date is prior to the year of the date of the last dose of double-blind study drug, then December 31 will be assigned to the missing fields.
- If the year of the incomplete stop date is after the year of the date of the last dose of double-blind study drug, then January 1 will be assigned to the missing fields.

Missing month only

- The day will be treated as missing and both month and day will be replaced according to the above procedure.

Missing day only

- If the month and year of the incomplete stop date are the same as the month and year of the date of the last dose of double-blind study drug, then the day of the date of the last dose of double-blind study drug will be assigned to the missing day.
- If either the year is before the year of the date of the last dose of double-blind study drug or if both years are the same but the month is before the month of the date of the last dose of double-blind study drug, then the last day of the month will be assigned to the missing day.

- If either the year is after the year of the date of the last dose of double-blind study drug or if both years are the same but the month is after the month of the date of the last dose of double-blind study drug, then the first day of the month will be assigned to the missing day.

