### **8.2.4. Clinical/Medication History**

The investigator or a qualified designee should review the patient's clinical history, including details relating to CF and any other medical conditions. Information regarding clinical history and current medications must be captured on the medical history and prior/concomitant medication CRFs, respectively. In particular, details regarding any inhaled aminoglycoside use

within 6 months prior to study entry should be documented. In addition, history of *Pseudomonas aeruginosa* infection, history of renal insufficiency, and history of exocrine pancreatic insufficiency should also be collected.

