4.8. Prior and Concomitant Medications and Procedures

Prior medications will be defined as those medications that were used prior to the first dose of study treatment. Concomitant medications will be defined as those medications that were used during the study treatment period. If the start date of a medication is missing and the end date is

prior to study start, the medication will be deemed prior. If the end date is after study start or is also missing, the drug will be deemed concomitant. If the end date is missing or the medication is ongoing, the medication will be considered concomitant. If the medication start date is completely missing and end date is missing or ongoing, the medication will be considered both prior and concomitant. Prior and concomitant therapies will be defined similarly.

Prior and concomitant medications will be coded by means of the World Health Organization Drug Dictionary (WHODRUG) into Anatomical-Therapeutic-Chemical classification (ATC) codes. Subject incidence of prior and concomitant medications will be tabulated by ATC level 2 and preferred term for the As-Treated population. Subjects will only count once for each ATC or preferred term in the event that they have multiple records of the same ATC or preferred term in the database.

Prior and concomitant non-drug therapies will be coded and analyzed similarly.

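### In one pattern of partial dates, SAP 5.5.2 replaces a medication's recorded pre-study stop month with the first-dose date

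*SAP*

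**What the plan says.** The rules for partial medication dates are in SAP 5.5.2, 5.5.2.1 and 5.5.2.2.

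- **Order.** SAP 5.5.2: "When the start date and the stop date are both incomplete for a subject, impute the start date first".
- **Start with only a year, equal to the first-dose year.** SAP 5.5.2.1: "then the day and month of the date of the first dose of double-blind study drug will be assigned to the missing fields". The start becomes the first-dose date.
- **Start with only a year, before the first-dose year.** For the case "If the year of the incomplete start date is prior to the year of the date of the first dose of double-blind study drug", the start becomes 31 December of the recorded year.
- **Start with month and year, before the first-dose month.** Here "then the last day of the month will be assigned to the missing day".
- **Check on the start.** The start is moved back to the stop date under one condition: "If the stop date is complete and the imputed start date is after the stop date". Nothing is said about a partial stop.
- **Stop with month and year, before the last-dose month.** SAP 5.5.2.2 gives the last day of the recorded month.
- **Check on the stop.** If the imputed stop falls before the start, "then the imputed stop date will be equal to the start date". The SAP states that this holds even when the start was itself imputed.

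Classification is in SAP 4.8: "Concomitant medications will be defined as those medications that were used during the study treatment period". The same section calls a drug prior if its start is missing and its end precedes the study, and concomitant if its end is missing. It does not say whether it works on recorded or imputed dates, or whether a partial date counts as missing.

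**The concern.** A recorded stop month is evidence; a start imputed from a year alone is a guess. Where the two conflict, SAP 5.5.2.2 lets the guess win. A drug known to have ended before the study can then carry first-dose day as both its start and its stop.

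Pre-study antibiotic records are expected in this trial. Protocol 8.2.4 says of the six months before entry: "In particular, details regarding any inhaled aminoglycoside use" should be documented. SAP 4.10.1 lists renal adverse events separately for subjects who did and did not use nephrotoxic concomitant medications. If those listings are built on imputed dates, a past course shown as Day 1 use could move a subject's renal event from the second listing to the first. The concomitant-medication table in SAP 4.8 could also count a drug that was only prior.

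**Working it through.** The SAP gives no figure here, so the check is to apply its rules literally. The dates are illustrative and are not in the documents: start 2015 (month and day unknown), stop March 2015 (day unknown), first dose 15 September 2015, last dose 2 March 2017. The anchor is read as ataluren in Study 023.

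1. The start is imputed first. Its year equals the first-dose year, so start = 15 September 2015.
2. The check in 5.5.2.1 needs a complete stop. The stop has no day, so the start stays.
3. March 2015 is before the last-dose month, so stop = 31 March 2015.
4. 31 March is before 15 September, so stop = 15 September 2015.

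The gap from 31 March to 15 September is 30 + 31 + 30 + 31 + 31 + 15 = 168 days. As 31 March is the latest day that fits the record, the drug ended at least 168 days before first dose. With imputed dates, SAP 4.8 makes it concomitant.

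Other patterns with the same first and last dose:

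| Start recorded | Stop recorded | Imputed start | Imputed stop | Class on imputed dates |
|---|---|---|---|---|
| 2015 | March 2015 | 15 Sep 2015 | 15 Sep 2015 | concomitant |
| 2015 | 20 March 2015 | 20 Mar 2015 | 20 Mar 2015 | prior |
| February 2015 | March 2015 | 28 Feb 2015 | 31 Mar 2015 | prior |
| 2014 | March 2015 | 31 Dec 2014 | 31 Mar 2015 | prior |
| 2014 | March 2014 | 31 Dec 2014 | 31 Dec 2014 | prior |

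Rows 1 and 2 differ only in whether the stop day was recorded, which has no bearing on whether the drug ended before the study. In the last row the stop also leaves its recorded month, but harmlessly, because the imputed start is still before first dose.

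The general condition follows. The overwritten stop equals the imputed start, so the class changes only if that start is on or after first dose. For a drug whose recorded stop month precedes the first-dose month, this needs a year-only start in the first-dose year.

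As confirmation, the rules were applied to every logical pair of start and stop months from January 2013, for a first dose on 15 October 2015 and a stop month before October:

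- year-only start in 2015: 45 of 45 pairs became concomitant;
- start month known in 2015: 0 of 45;
- start in an earlier year: 0 of 1,032 (516 year-only plus 516 with a known month).

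The pattern cannot arise for a January first dose. The largest possible shift is from 31 January to 31 December of the same year, 365 - 31 = 334 days.

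**The case against.** **SAP 4.8 may already settle the case.** It calls a drug with a missing start and a pre-study end prior. It elsewhere speaks of a completely missing start, which suggests that plain missing can include partial. Applied to recorded dates, March 2015 would then be prior. This stands as a possible reading, so the classification error is conditional. It is not a clear rescue. If partial counts as missing for the start, it should also count for the stop, and SAP 4.8 makes a drug with a missing end concomitant. The favourable result needs the partial start treated as missing and the partial stop as known, which the SAP does not say.

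**The anchor is ambiguous.** The rules refer to double-blind drug, but Study 023 is open-label (Protocol 14.1.1). If the anchor were dosing in Study 009, whose results are cited from 2012, the example would give 1 January to 1 March 2015, which is prior. Reading it as ataluren in Study 023 is plausible, but it is an assumption.

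**The consequences are limited.** SAP 4.2 describes all analyses as descriptive. Adverse event counts, laboratory values, FEV1 and exposure-adjusted rates do not use medication dates in this way. SAP 4.10.1 does not define the renal listings by imputed dates. All of this stands.

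**Stronger readings that the documents do not support:**

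- A reader might infer that any record with two partial dates is misclassified. The working shows that this needs the specific pattern.
- A reader might turn the number of eligible stop months into a share of records. The documents give no count of such records and no distribution of first-dose months.
- A reader might expect the same fault in SAP 5.5.1. That section imputes only start dates, and Protocol 9.8 starts adverse event reporting at first dose, so an event that ended earlier should not be in the data.

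**Conclusion.** The point holds in narrow form. For a start with unknown month in the first-dose year and a stop with a known earlier month in that year, SAP 5.5.2 discards the recorded stop month and puts both dates on first-dose day. The stop moves by at most 334 days, and by at least 168 in the example.

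Two assumptions carry this: the anchor means ataluren in Study 023, and SAP 4.8 is applied after imputation. Under them the drug is wrongly concomitant. Without the second, the class is undetermined by the text. What can be affected is the concomitant-medication table and, only if built on imputed dates, the renal listings by nephrotoxic medication. The number of affected records may be small. It is worth correcting because a stated rule contradicts recorded data.

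**What to change.** Four wording changes in the SAP:

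1. In 5.5.2.1, extend the check to a partial stop with a known month: the imputed start may not fall after the imputed stop. When the stop month precedes the first-dose month, that stop is the last day of its recorded month. The comparison is made once both values have been derived.
2. In 5.5.2.2, state that setting the stop equal to the start may never move a stop out of its recorded month or year.
3. In 4.8, state that the classification uses the dates resulting from 5.5.2.
4. Throughout 5.5.2, name ataluren in Study 023 as the anchor drug.

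The example then returns 31 March 2015 for both dates, which is prior and agrees with the complete-date record.

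The stop should not be capped at last dose. For a drug recorded as April 2017 to April 2017 with last dose 2 March 2017, the present rules give 1 April to 1 April, after treatment. A cap, with the start held no later than the stop, would give 2 March to 2 March: a post-treatment drug on a treatment day, with both dates outside their recorded month. No change to 5.5.1 is needed.

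The cost is a few sentences and a small programming change, with no new data. SAP section 1 allows refinements by amendment before database lock.

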5.6. Pulmonary Exacerbation Definitions

A respiratory event evaluation form has been developed to collect CF pulmonary exacerbation information from the physician perspective. This form is designed to systematically characterize health-care provider observations related to exacerbations, and to allow categorization and scoring consistent with Fuch's or Rosenfeld CF exacerbation definitions. The data generated from these forms will provide the basis for recording incidence and rate of pulmonary exacerbations.

The following 12 Fuchs' signs and symptoms will be assessed in the definitions of Fuch's, modified Fuch's, and expanded Fuch's exacerbation.

1. Increased cough
2. Change in sputum volume, color, or consistency
3. New or increased hemoptysis
4. Increased dyspnea during moderate exertion, during mild exertion, or at rest
5. Sinus pain or tenderness
6. Change in sinus discharge
7. Malaise, fatigue, or lethargy
8. Anorexia or weight loss
9. Temperature above 38°C
10. Change in findings on chest examination
11. Relative 10% decrease in %-predicted FEV₁
12. Chest radiography results consistent with pulmonary infection

The modified Fuchs exacerbation is defined as the presence of at least 4 of 12 Fuchs' signs and symptoms without the requirement for treatment with antibiotics [Rowe 2012].

The expanded Fuchs exacerbation is defined as the presence of at least 4 of 12 Fuchs' signs and symptoms requiring treatment with any form of antibiotic treatment [inhaled, oral, or intravenous]. This antibiotic treatment is defined either as the addition of new antibiotics or an increase in the dose of an existing antibiotics within 14 days of the pulmonary exacerbation start/stop date.

The classic Fuchs exacerbation is defined as the presence of at least 4 of 12 Fuchs' signs and symptoms requiring treatment with parenteral antibiotics. This antibiotic treatment is defined either as the addition of new antibiotics or an increase in the dose of an existing antibiotics within 14 days of the pulmonary exacerbation start/stop date.

Pulmonary exacerbation based on investigator's assessments is recorded in the conclusion of respiratory event evaluation form.

6. ANALYSIS CHANGES FROM PROTOCOL

Due to the premature termination of the study, the time of withdrawal from the study analysis has been removed compared to current protocol version 3.0. The paired t-test on FEV₁ and the summary of FEF₂₅₋₇₅ have also been removed. On the other hand, the drug exposure adjusted incidence rate of TEAEs has been added. Summary of occurrence of TEAE has been added as well.

